## Research Summary – Inhaled Pulmonary Vasodilators in Thoracic Transplantation & LVAD Surgery

hours after lung transplantation. The primary endpoint for the comparison of efficacy in LVAD patients will be incidence of moderate or severe RV failure according to Interagency Registry for Mechanically Assisted Circulatory Support (INTERMACS) scoring. The primary endpoint for the comparison of efficacy in the heart transplant subset will be the incidence rate of RVAD insertion. Secondary endpoints related to clinical outcomes for all populations will be duration of postoperative mechanical ventilation, ICU Length of Stay (LOS), hospital LOS, incidence of acute kidney injury, incidence of in-hospital mortality, as well as postoperative mortality at 30-days, 90-days, and 1-year after operation (Table 1).

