**11. Data Analysis & Statistical Considerations:** Summary statistics will be computed for demographic, clinical, and outcome variables in the form of frequencies (percentage) for categorical variables and mean (standard deviation) for continuous variables for each arm. Univariate analysis will be performed to compare the difference of each variable between treatment groups by chi-square or Fisher exact tests for categorical variables, and t-tests or Wilcoxon Rank-Sum tests for continuous variables depending on data normality. The univariate results for the outcome variables will provide information on iNO treatment effect in comparison to iEPO without taking into account other potential confounding factors. All non-outcome variables meeting  $p < 0.15$  association with treatment group will be considered for variable selection to build a multivariable regression model. For each outcome of interest, we will start with a regression model (logistic regression for binary outcomes or generalized linear model for continuous outcomes) with all variables selected from univariate analysis described above. Based on stepwise variable selection, we will determine the final set of covariates to be included in the final multivariable model to test the treatment group effect. Based on the analysis results, we will be able to understand if iNO is equivalent to iEPO (no significant difference) or significantly better or worse than iEPO (significant treatment effect) to address the efficacy of iNO for Aim 1. Several of secondary measures will be obtained over time. We will apply generalized mixed model to take into account the repeated measures over time to test for treatment effect. In the case of patients have switched to the other arm due to clinical decision, we will conduct the primary analysis based on the intent to treat (ITT) without reclassifying treatment assignment. In addition, protocol analysis, where only patients follow the protocol assignment are included will also be conducted to verify ITT results. For Aim 2 to compare cost capture analysis, the comparison of cost measures between two groups will be tested by two sample t-test.

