Based on recent *annual* operations, approximately 120 LVAD implantations, 60 heart transplantations, and 110 Lung transplantations were performed at Duke University Hospital during FY 2014 – 2015. This study has been individually powered to primary endpoints for each arm (Table 1) and the duration of study enrollment has been determined according to annual operations and sample-size calculations. We estimated sample size based on equivalence test of the incidence rates of a binary outcome (e.g. PGD grade 3 (PGD-3)) of two treatment groups as an illustration. Assuming the incidence rate of PGD-3 under iEPO treatment is 0.35 and acceptable margin of the equivalence is  $\pm 0.19$ , we will need 224 patients to have 80% power to detect an actual difference at 0.05 between two treatment group under this margin. This implies that the acceptable range of incidence rate for iNO treatment is from 0.21 to 0.59. Based on this estimate, we propose to enroll 200 lung transplant patients and 224 LVAD and heart transplant patients ( $n = 424$ ) over a period of 24 to 36 months; the exact time point for trial culmination between 24 and 36 months will be dependent on enrollment rate. There will be a 50% randomization rate for each inhaled agent such that 212 patients will receive iEPO and 212 patients will receive iNO.

**12. Data & Safety Monitoring:** The proposal is not introducing a new medication that has not been utilized by our group and safety has been established for this patient population through clinical practice and medication usage. Safety will, however, be determined by assessing reported, rare, adverse effects of iNO (systemic hypotension, methemoglobinemia, and rebound pulmonary hypertension after appropriate weaning) and iEPO (systemic hypotension, non-surgical bleeding related to thrombocytopenia, flushing, and rebound pulmonary hypertension after appropriate weaning) in order to accurately monitor adverse events (AE) during this study. The PI will review and sign off on AE's as they occur and perform a quarterly review and determine if AE's are related to the study or otherwise. AE's will be reported to the IRB per HRPP policies.

*Stopping Rule:* Subjects who meet the stopping criteria in section 4 continued to be enrolled and followed for primary outcome analysis. See section 4 for stopping criteria.

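### Section 11 applies its equivalent / better / worse verdict to every outcome instead of the primary endpoints only, so the eight secondary endpoints can yield unsupported claims

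*Combined protocol and SAP*

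**What the plan says.** The analysis rule is in Section 11, Data Analysis & Statistical Considerations. It opens with "For each outcome of interest, we will start with a regression model", then selects covariates stepwise and tests the treatment effect in the final model. The reading of that test follows: "Based on the analysis results, we will be able to understand if iNO is equivalent to iEPO (no significant difference) or significantly better or worse". The sentence ties the result to the efficacy question of Aim I. Nothing in it separates primary from secondary outcomes.

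The secondary endpoints are listed in Section 4, Measured Outcomes: "Secondary endpoints related to clinical outcomes for all populations will be duration of postoperative mechanical ventilation, ICU Length of Stay (LOS), hospital LOS", followed by "incidence of acute kidney injury, incidence of in-hospital mortality, as well as postoperative mortality at 30-days, 90-days, and 1-year after operation". Table 1 gives the same list for all populations. Section 11 adds, for secondary measures taken repeatedly: "We will apply generalized mixed model to take into account the repeated measures over time to test for treatment effect".

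On power, Section 11 says "This study has been individually powered to primary endpoints for each arm", and the footnote to Table 1 agrees that the sample size serves the primary outcomes. The ±0.19 margin appears once, in the sample size illustration for grade 3 PGD.

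**The concern.** Section 2 makes a similar impact on clinical outcomes part of the primary hypothesis, and Section 4 describes the eight secondary endpoints as relating to clinical outcomes. A verdict rule that covers every outcome of interest therefore lets any one of the eight feed the Aim I conclusion. Two errors can follow.

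- **False difference.** With eight tests and no limit on what may be claimed, one nominally significant length-of-stay or mortality result could be reported as one drug being significantly better, even if the drugs are identical.
- **False equivalence.** A secondary endpoint that is merely non-significant would be called equivalent, although no margin has been set for it and the trial was not sized for it.

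The plan has no multiplicity rule, testing order or statement that secondary results are supportive, any of which would restrain these claims.

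**Working it through.** **The plan's own figure.** There is none to reproduce. The documents give no error rate for the secondary endpoints and no significance level for any outcome test. The 0.05 in the sample size text, "we will need 224 patients to have 80% power to detect an actual difference at 0.05 between two treatment group under this margin", is worded as a true difference. The p < 0.15 threshold is for screening covariates.

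**Inputs.**
- Secondary endpoints: ventilation duration, ICU stay, hospital stay, acute kidney injury, and mortality in hospital, at 30 days, at 90 days and at 1 year. That is 3 + 1 + 4 = 8 (Section 4; Table 1).
- Populations: two strata, from "we propose to enroll 200 lung transplant patients and 224 LVAD and heart transplant patients" (Section 11).
- Assumed: two-sided 0.05 per test, no true difference on any endpoint, one common correlation r among the eight test statistics, and independence between populations.

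**Step 1: each endpoint tested once.** With r = 0, the chance of at least one false verdict is 1 − (1 − 0.05)^8 = 1 − 0.663 = 0.337. With r > 0, the chance is 1 minus the average, over a standard normal u, of [Φ((1.96 − √r·u)/√(1−r)) − Φ((−1.96 − √r·u)/√(1−r))]^8. Numerical integration gives 0.250 at r = 0.5 and 0.157 at r = 0.8.

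**Step 2: each endpoint tested separately in two populations.** The chance is 1 − (1 − f)², where f is the result of step 1.

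| Common correlation | Tested once | Tested in each of two populations |
|---|---|---|
| 0 | 0.337 | 1 − 0.663² = 0.560 |
| 0.5 | 0.250 | 1 − 0.750² = 0.438 |
| 0.8 | 0.157 | 1 − 0.843² = 0.290 |

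**Step 3: a less uniform structure.** The four mortality measures overlap, and the three duration measures are linked. A simulation with those links used assumed mortality of 4% to 12%, assumed kidney injury of 40%, and Fisher's test for sparse counts. It gave 24% to 25% per population and about 43% across the two. That agrees with the r = 0.5 row.

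**Step 4: the equivalence half of the rule.** Take the lung stratum, 200 patients at 1:1, so 100 per arm, and the same assumed mortality of 4% to 12%. If the two arms show identical mortality p, the approximate 95% confidence interval for the difference is ±1.96 × √(2p(1−p)/100):
- p = 0.04: 1.96 × √0.000768 = 0.054
- p = 0.12: 1.96 × √0.002112 = 0.090

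Even with no observed difference, the data would leave open a true difference of roughly 5 to 9 percentage points. The written rule would call that result equivalent. The interval is rough at such low counts, but its order of size is enough for the point.

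**The case against.** The strongest reply is that the plan does rank its endpoints. Table 1 and Section 4 label them primary and secondary, power is stated only for the primaries, and Data Collection calls the haemodynamic variables secondary measures. That is fair, and it rules out saying that the plan gives secondary results equal standing. But a label does not say which results may support an Aim I claim, and the verdict rule in Section 11 ignores the label.

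Three stronger readings are tempting, and the documents do not support them.

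- **That the secondaries are confirmatory tests at full alpha.** The plan never calls them confirmatory and states no alpha. The 0.05 used here is an assumption.
- **That a false difference is about as likely as not.** Each endpoint tested once gives at most 34%. Figures near one half need separate testing in two populations, counted as one family, and Section 4 says only that the endpoints apply to all populations. A further split of heart transplant from LVAD patients would raise the rate to 58% at correlation 0.5, but no text states that split for secondary endpoints.
- **That the repeated measures belong in the same family.** Adding the ten haemodynamic variables of Table 2 would raise the rate further. But Section 11 deals with repeated measures after the verdict sentence and attaches no such verdict to them, and Table 2 includes LVAD flow, which does not exist for lung recipients.

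It can also be said that a spurious difference works against the trial's hoped-for conclusion of similarity. That is true of the false-difference half of the rule. The false-equivalence half works in favour of that conclusion.

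**Conclusion.** The point holds in a limited form. Section 11 states one verdict rule for every outcome of interest and does not confine it to the primary endpoints, which alone are powered. At an assumed two-sided 0.05 per test with no true differences, the eight secondary endpoints carry about a 25% chance of at least one false better-or-worse verdict if each is tested once (16% to 34% for correlation 0.8 to 0). If they are tested in each of two populations instead, the chance is about 44% (29% to 56%); that condition is implied, not stated. The lowest of these, 16%, is about three times 0.05.

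These figures leave out the univariate, adjusted and per-protocol repeats of each comparison and the stepwise covariate selection, all in Section 11, which add further chances of a false finding. The equivalence half of the rule needs no alpha assumption to fail: no margin exists for any secondary endpoint. This is a cheap improvement to the wording and does not challenge the design.

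**What to change.** In Section 11, restrict the equivalent / significantly better or worse verdict to the primary endpoints. Add that all secondary endpoints and all repeated secondary measures are supportive. They should be reported as effect estimates with 95% confidence intervals, and no claim of equivalence, superiority or inferiority should be made from them.

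A multiplicity adjustment alone (for example 0.05/8 = 0.00625 per endpoint) would limit false differences but would make non-significance, and so a call of equivalence, more likely. Limiting the verdict deals with both errors.

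The cost is one or two sentences, and secondary results can no longer support stand-alone claims. Data, sample size and procedures do not change.

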**Table 1. Study Summary**

§Sample Size	N = 424 (50/50 by randomization strata)
Population	1. Lung transplantation (N = 200) 2. Heart Transplantation / LVAD implantation (N = 224)
Rationale	
 
• Comparison of iNO and iEpo impact on outcomes – evaluate for equivalency
 
• PVD therapy indications:               
 
1. Lung Transplant: Improvement of ventilator and perfusion matching after lung allograft implantation by vasodilation of ventilated pulmonary capillaries
 
2. Heart Transplant/LVAD Implantation: Improvement of RV contractility after cardiac allograft implantation or LVAD implantation by PVR reduction
 
 
 

Study Design	Prospective, Randomized, Double-Blinded
Primary Outcomes	1. Lung Transplant: Severe PGD (grade 3) 2a. Heart Transplant: RVAD insertion b. LVAD: INTERMACS Moderate or Severe RVF
Secondary Outcomes	All populations: 
 
• ICU LOS (days)
 
• Hospital LOS (days)
 
• Mechanical ventilator duration (hours)
 
• Postoperative AKI
 
• In-hospital mortality
 
• Mortality 30-day, 90-day, 1-year
 

Study length*	24-36 months

§Sample size powered for primary outcomes

\*Study length is determined through sample size divided by annual operations at Duke University Hospital; AKI = Acute kidney injury; iEpo = inhaled epoprostenol; iNO = Inhaled nitric oxide; ICU = Intensive care unit; LOS = Length of stay; LVAD = Left ventricular assist device; PGD = Primary graft dysfunction; PVD = Pulmonary vasodilators; PVR = Pulmonary vascular resistance; RVF = Right ventricular failure

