## Research Summary – Inhaled Pulmonary Vasodilators in Thoracic Transplantation & LVAD Surgery

which require reliable gastrointestinal absorption that may not be present during high-dose inotropic support, and are not readily titrated to effect as are the inhaled PVD, iNO and iEPO.

**Contraindications and Adverse Effects.** Absolute indications for iNO in favor of iEPO are due to prostaglandin allergy leading to anaphylaxis (extremely rare) or if the patient is pregnant due to risk for labor induction as a result of prostacyclin agonism. Routine pregnancy testing is performed in the preoperative setting in line with established preoperative anesthesia testing criteria. Parturients rarely present for thoracic transplantation or LVAD implantation. There are no absolute contraindications to iNO therapy in adult patients but the iNO delivery device system routinely measures the toxic metabolite of iNO, nitrogen dioxide (NO2), which can lead to hypoxemia during metabolite accumulation. Additionally, methemoglobinemia (MetHb) is another rare adverse occurrence of prolonged iNO administration and MetHb levels are measured during arterial blood gas analysis.

**Preliminary retrospective study supporting noninferiority hypothesis.** In a retrospective study of 51 adult cardiothoracic surgical patients (all-comers, including thoracic transplantation, durable LVAD implantation, and non-transplant and non-LVAD cardiac surgical patients), requiring pulmonary vasodilation, our group illustrated similar efficacy between the use of iEPO and iNO with respect to optimizing RV hemodynamic variables,

including pulmonary vasodilation and mixed venous oxygenation (Table 2). During this investigation, iNO was initiated in the operating room (OR) and continued during transport and into the ICU. While in the ICU, postoperative hemodynamic stability was achieved within 2 hours and iNO was transitioned to iEPO over 30 minutes in order

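### The analysis declares equivalence when a difference test is non-significant, and never uses the ±0.19 margin on which the trial was sized

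*Combined protocol and SAP*

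**What the plan says.** Similar efficacy and similar clinical impact form the primary hypothesis (section 2), and Table 1 gives the rationale as "Comparison of iNO and iEpo impact on outcomes – evaluate for equivalency".

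The sample-size part of section 11 follows that aim: "We estimated sample size based on equivalence test of the incidence rates of a binary outcome". It begins "Assuming the incidence rate of PGD-3 under iEPO treatment is 0.35", sets a margin of ±0.19, and asks for 224 patients for 80% power. It adds: "This implies that the acceptable range of incidence rate for iNO treatment is from 0.21 to 0.59". Enrolment is then set at 200 lung patients and 224 heart transplant or LVAD patients.

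The analysis part of section 11 takes another route. Binary outcomes are compared "by chi-square or Fisher exact tests for categorical variables". A stepwise regression then yields the "final set of covariates to be included in the final multivariable model to test the treatment group effect". The only rule for the efficacy conclusion is: "we will be able to understand if iNO is equivalent to iEPO (no significant difference) or significantly better or worse than iEPO".

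The margin appears only in the sample-size text. No two one-sided tests (TOST), no comparison of a confidence interval with a margin, and no clearly stated alpha appear anywhere. The subheading in section 3, "Preliminary retrospective study supporting noninferiority hypothesis", names yet another kind of hypothesis.

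**The concern.** The two halves of section 11 define equivalence differently. Under the sample-size half, the data must exclude differences as large as the margin. Under the analysis half, it is enough that the data fail to exclude zero. The second rule rewards weak data: the smaller or noisier the trial, the easier it is to conclude equivalence.

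This is the trial's main claim, and it is meant to support using one drug in place of the other. An inconclusive result could be reported as evidence that the drugs are interchangeable. The false-equivalence rate is not controlled, and the stated 80% power belongs to a test the plan does not perform.

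Three gaps make the rule hard to repair by inference:
- The margin is on the risk-difference scale, whereas the final model is logistic.
- The margin itself is stated inconsistently.
- INTERMACS right ventricular failure and RVAD insertion have no stated rate or margin.

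**Working it through.** **Inputs from section 11.** iEPO rate 0.35; margin ±0.19; 0.05, worded as the actual difference; 80% power; 224 patients; 1:1 allocation; 200 lung patients, so 100 per arm.

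**Assumptions, because the plan is silent.** Difference test at two-sided 0.05; TOST at one-sided 0.05 each, i.e. a 90% Wald interval inside the limits; no dropout.

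**The margin.** 0.35 ± 0.19 is 0.16 to 0.54. The printed range, 0.21 to 0.59, is 0.40 ± 0.19. As limits for iNO minus iEPO with iEPO at 0.35, the printed range is −0.14 to +0.24.

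**Reproducing 224.** With lower limit L, upper limit U and true difference d, the normal approximation is

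power = Φ((U − d)/SE − 1.645) + Φ((d − L)/SE − 1.645) − 1.

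At 0.35 vs 0.40 and 112 per arm, SE = √((0.35×0.65 + 0.40×0.60)/112) = 0.0646.
- Printed range: both distances are 0.19, so each term is Φ(0.19/0.0646 − 1.645) = Φ(1.296) = 0.9025. Power = 2×0.9025 − 1 = 0.805, which matches 224 patients and 80%.
- ±0.19 around 0.35: Φ(0.14/0.0646 − 1.645) + Φ(0.24/0.0646 − 1.645) − 1 = 0.68, short of 80%.
- If 0.05 is instead alpha and the true difference is zero, ±0.19 gives 0.82 at 224 patients.

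**Comparing the rules.** For each pair of true rates I summed the exact binomial probabilities of all outcomes meeting each rule, at 100 per arm:

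| True iEPO vs iNO | Limits | Stated rule says equivalent | TOST says equivalent |
|---|---|---|---|
| 0.35 vs 0.54 | ±0.19 | 21.2% (Fisher 25.6%) | 4.8% |
| 0.35 vs 0.16 | ±0.19 | 12.2% | 5.1% |
| 0.35 vs 0.59 | −0.14 to +0.24 | 6.4% | 4.7% |
| 0.35 vs 0.21 | −0.14 to +0.24 | 39.9% | 5.0% |
| 0.35 vs 0.40 | ±0.19 | 88.7% | 62.0% |
| 0.35 vs 0.40 | −0.14 to +0.24 | 88.7% | 73.9% |

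At 0.35 vs 0.40, the stated rule says equivalent without the data excluding the limits in 26.7% of trials with ±0.19, and in 15.1% on the printed range.

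At 0.35 vs 0.54, the stated rule's false-equivalence rate is 21.2% at 100 per arm, 49.7% at 50 and 79.0% at 20.

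**One possible result.** Take 35/100 on iEPO and 48/100 on iNO; the difference is 0.13.
- Pooled SE = √(2×0.415×0.585/100) = 0.0697, z = 1.87, p = 0.062. The stated rule says equivalent.
- Unpooled SE = √((0.35×0.65 + 0.48×0.52)/100) = 0.0691. The 90% interval is 0.13 ± 1.645×0.0691 = 0.016 to 0.244, beyond both 0.19 and 0.24. The equivalence test says not shown.

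**The case against.** The best defence is that the sample-size text implies a margin-based test, and that the analysis sentence is loose wording. The printed range supports this: with a true difference of 0.05 and one-sided 0.05, it reproduces 224 patients and 80% power. That is good evidence of what the designers had in mind, and it makes the literal reading of 0.05 as the true difference the likelier one. It does not rescue the plan, because the analysis text supplies its own definition of equivalence, and that definition contradicts the margin. Nor does this reading favour the stated rule: false equivalence is then 6% at one limit but 40% at the other, where iEPO has the higher PGD-3 rate.

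Other points stand in part:
- The calculations use an unadjusted chi-square test, whereas the plan ends with a stepwise model whose behaviour was not computed. The figures illustrate the rule rather than give its exact properties. The model still ends in a test of no difference, so the logic is unchanged.
- The PGD-3 calculation is offered as an illustration. Enrolment is nevertheless set from it, and power is claimed for each primary endpoint.
- The non-inferiority wording is a background subheading about a retrospective study. It is a minor inconsistency.

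**Conclusion.** The concern holds and must be fixed before analysis. As written, the plan can declare equivalence on its main hypothesis from data that do not exclude differences beyond its own margin. At the limits of acceptability, with 100 per arm, the stated rule is wrong in 12% to 21% of trials with ±0.19 around 0.35, and in 6% to 40% on the printed range. TOST holds each of these near 5%. The sizes rest on the assumed alpha, the iEPO rate of 0.35, no dropout and an unadjusted test. The logical error depends on none of them.

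**What to change.** Replace the rule in section 11 with wording such as:

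*For PGD-3, equivalence is concluded only if the two-sided 90% confidence interval for the risk difference (iNO minus iEPO) lies wholly within the pre-specified margin. A difference is claimed only if the 95% confidence interval excludes zero. If both hold, a significant difference within the margin is reported. If neither holds, the result is inconclusive.*

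The 90% level corresponds to one-sided 0.05; if the sponsor states another alpha, the interval should match it. In addition:
- Name one deciding estimate. I suggest the direct risk difference in the intention-to-treat set, already the plan's primary set, with a risk difference standardised from the logistic model as support. State how the per-protocol result bears on the claim.
- Reconcile ±0.19 with the range 0.21 to 0.59, state alpha, and say whether the claim is equivalence or non-inferiority.
- Restate power for 200 lung patients.
- For right ventricular failure and RVAD insertion, justify an endpoint-specific margin or make no equivalence claim.
- For secondary outcomes, report estimates with confidence intervals and claim no equivalence.

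**Cost.** No new data are needed, but fewer trials end in equivalence. At 0.35 vs 0.40, 100 per arm and ±0.19, about 62% conclude equivalence, 11% a difference and 26% neither; the stated rule calls 89% equivalent. Power at 100 and 112 per arm is 62% and 69% with ±0.19, 74% and 80% on the printed range, and 76% and 82% with ±0.19 if the true difference is zero. With ±0.19 and 0.35 vs 0.40, exact power first reaches 80% at 147 per arm but dips below it again until 151, so about 300 lung patients would be needed.

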### 2. Purpose of the Study:

**1. Aim I – Clinical Trial Investigation.** In order to utilize Inhaled Epoprostenol (iEPO, Veletri®, Actelion Pharmaceuticals, South San Francisco, CA, USA) as an acceptable alternative to Nitric Oxide (iNO, INOMAX®, Mallinkrodt Pharmaceuticals, St. Louis, MO, USA) in adult patients, we propose a randomized, prospective, double-blinded trial in the cardiothoracic surgical population, which will evaluate the primary hypothesis that these two medications will have similar efficacy in pulmonary vasodilation and a similar impact on clinical outcomes in end-stage lung disease patients undergoing lung transplantation and end-stage heart failure patients under durable LVAD implantation or heart transplantation (Table 1).

**2. Aim II – Cost-Capture Analysis.** There will be a parallel prospective cost-capture analysis designed to precisely acquire the expenses that each drug incurs per patient averaged across all patients randomized to that drug.

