### 4. Design & Procedures:

#### Aim I – Development of a Definitive Clinical Trial Investigation.

**1. Randomization and Double-Blinding.** The clinical research unit (CRU) will receive preoperative notification of lung and heart transplantation patients by reviewing the transplant waitlist. Preoperative notification of LVAD implantation will be done by the review of the cardiothoracic surgical schedule. Using a 50% randomization process utilized and established by the CRU at Duke University Hospital, each eligible patient will be randomized to receive either iNO or iEPO. The primary endpoint data will be collected and documented in an electronic data capture system during the period of time the patient, clinical care team, and study team are blinded. Primary endpoint data collection will be complete prior to the subjects' discharge from the ICU, at which point the unblinding will occur. Since primary endpoint data collection will occur during the blinded period, the potential for bias will be substantially minimized.

**2. Measured Outcomes.** The primary endpoint for the comparison of efficacy in the Lung Transplant population will be the incidence of Grade 3 Primary Graft Dysfunction (PGD). This is defined by the International Society of Heart and Lung Transplantation (ISHLT) as severe hypoxemia with a PaO2-to-FiO2 ratio < 200 or the presence of venovenous extracorporeal membrane oxygenation (VV ECMO) at a time-point within the first 72

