### Aim II – Cost-Capture Analysis.

In parallel with the design & procedures of *Aim I*, the cost capture analysis component will be essential in order to better gauge the cost due to duration of administration (variable cost) according to each inhaled PVD. Established clinical criteria specific to each group (lung transplantation vs. heart transplantation/LVAD implantation) have been developed to determine the inception of protocolized PVD weaning. Weaning medications according to established protocols will allow for accurate interpretation of the comparative length of therapy between iNO and iEPO and help prevent erroneous PVD usage without criteria for discontinuation. Secondary resource utilization will be documented by respiratory care services and itemized cost sheets will be developed.

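### The Aim II cost t-test does not use the randomisation strata, so its interval may be wider than the design warrants, and no cost difference is planned for lung or heart/LVAD patients separately

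*Combined protocol and SAP*

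**What the plan says.** Section 11 gives Aim II one sentence of analysis: "the comparison of cost measures between two groups will be tested by two sample t-test". It states no stratum term, confidence interval, alpha, cost standard deviation or analysis by population. A single pooled test is the natural reading, though the sentence does not say so outright.

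Section 2 defines the target as the "expenses that each drug incurs per patient averaged across all patients randomized to that drug". That is an all-patient mean for each drug.

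On allocation, Table 1 says "50/50 by randomization strata" and lists two populations, 200 lung and 224 heart transplant/LVAD, without naming the strata. Section 4 (Aim I, item 1) says only "Using a 50% randomization process utilized and established by the CRU", and Section 8 is similar; neither gives a stratification factor. Section 11 expects that "212 patients will receive iEPO and 212 patients will receive iNO".

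On what drives cost, the Aim II part of Section 4 treats duration of administration as the variable cost and bases the start of weaning on "Established clinical criteria specific to each group (lung transplantation vs. heart transplantation/LVAD implantation").

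**The concern.** If each population is split 50/50 between the drugs, a difference in mean cost between lung and heart/LVAD patients cannot enter the treatment comparison, because both arms contain the same mix. An unstratified t-test still puts that difference into its variance estimate. The standard error then exceeds the true sampling variation of the difference, and the interval is too wide.

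The second issue is usefulness. Cost is roughly an hourly rate times hours. If hours differ by population, the saving per patient differs as well, and one pooled figure describes neither group. A health system with a different case mix could not apply it directly.

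**Working it through.** **Arm sizes.** With 50/50 allocation in each population, 200/2 + 224/2 = 100 + 112 = 212 per arm, which matches Section 11.

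**Excess width in general.** Let w = 200/424 = 0.472 be the lung share, and d the gap in mean cost between populations in within-population standard deviations (SD), with equal SDs. With exact balance, the ratio of the t-test standard error (SE) to the stratified one is

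sqrt(1 + w(1 − w)d²), where w(1 − w) = 0.472 × 0.528 = 0.249.

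The actual two-sided error of a nominal 5% test is 2 × [1 − Φ(1.96 × ratio)]. The sample size giving the same precision with stratification is 424/ratio².

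| d (assumed) | SE ratio | Excess width | Actual error | Equivalent N |
|---|---|---|---|---|
| 0 | 1.000 | 0% | 0.050 | 424 |
| 0.25 | 1.008 | 0.8% | 0.048 | 417 |
| 0.5 | 1.031 | 3.1% | 0.043 | 399 |
| 1 | 1.118 | 11.8% | 0.028 | 339 |
| 2 | 1.413 | 41.3% | 0.006 | 212 |

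Simulation with 100 + 112 patients per arm (8,000 trials per setting) gave error rates of 0.050, 0.039, 0.031 and 0.005 at d = 0, 0.5, 1 and 2. Where the stratified test had about 80% power, the t-test had 0.80, 0.79, 0.72 and 0.51.

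**In cost terms.** Section 3 gives $14.83 per hour for iEPO and $95 to $115 for iNO; I use the midpoint, $105. Assume hours have a coefficient of variation of 0.7 and a heart/LVAD mean of 72 h. Let L be the lung mean. For hours:

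- within-population variance = 0.49 × (0.472 L² + 0.528 × 72²)
- between-population variance = 0.249 × (72 − L)²

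The hourly rate scales both parts equally within an arm, so it cancels from the ratio.

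| Lung mean (h) | Within | Between | SE ratio |
|---|---|---|---|
| 24 | 1,475 | 574 | 1.18 |
| 36 | 1,642 | 323 | 1.09 |
| 48 | 1,874 | 144 | 1.04 |
| 60 | 2,174 | 36 | 1.01 |

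**Would significance change?** Take the widest gap, 24 against 72 h. Mean hours are 0.472 × 24 + 0.528 × 72 = 49.4, so the pooled saving is (105 − 14.83) × 49.36 = about $4,450. The t-test SE is sqrt[(105² + 14.83²) × (1,475 + 574)/212] = about $330, so z is about 13.5. The stratified SE is sqrt[(105² + 14.83²) × 1,475/212] = about $280. The 95% half-widths are about $646 and $548. Both intervals are far from zero.

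**Dependence on the mix.** In the same scenario the savings are 90.17 × 24 = $2,164 for lung and 90.17 × 72 = $6,492 for heart/LVAD. The trial mix (47:53) gives $4,450. The annual volumes in Section 11 (110 lung against 120 + 60 = 180 heart/LVAD, or 38:62) give $4,850, which is 9% more. With equal hours in both populations there is no gap.

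**The case against.** The case against is substantial, and most of it stands.

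- **The excess is conditional.** It requires randomisation stratified by lung against heart/LVAD. The only support is a parenthesis in Table 1 that names no strata. Under simple randomisation the t-test SE is valid, and stratification would only add precision.
- **The gap is unknown.** Group-specific weaning criteria make different durations plausible, but no duration or cost by population is given. Only a few percent is at stake unless the gap is large.
- **The error is on the safe side.** A reader might infer that the planned test could produce a false claim of a cost difference. It could not for this reason: the error rate falls below nominal.
- **The mix is not a bias.** A reader might infer that the result is distorted by the 200:224 split. It is not. Under balanced allocation the mix is the same in both arms, and Section 2 declares the all-patient average as the target. Only interpretation is limited, and only if savings differ by population.

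One possible defence does not help. Section 11's multivariable modelling might be thought to adjust for population, but the Aim 2 sentence names the t-test alone. The modelling also screens covariates by association with treatment group at p < 0.15, and a factor balanced by design would not pass that screen.

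**Conclusion.** A minor point that holds conditionally. The plan names an unstratified t-test for cost although Table 1 indicates allocation within strata. If those strata are the two populations and their mean costs differ, the interval is conservative, by about 3% at a gap of 0.5 SD and 12% at 1 SD. The documents do not show which of these applies, or whether the gap is nearer zero. The estimate is unbiased for the declared target. At the protocol's hourly rates, with the hours assumed above, the conclusion on significance would not change. What the plan lacks is an interval that matches the design and a cost difference for each population.

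**What to change.** 1. Name the randomisation strata in Sections 4 and 11, consistently with Table 1.
2. Keep the all-patient difference in mean cost as the Aim II target. Estimate it as a stratum-weighted difference in means, or from a linear model with treatment, stratum and their interaction, averaged over the strata. Give a confidence interval from the stratified variance or a bootstrap within strata.
3. Report the cost difference separately for lung and for heart/LVAD.

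A model with treatment and stratum main effects alone is not enough. Because cost is rate times hours, the lung-to-heart gap is about seven times larger under iNO (105/14.83 = 7.1), and that interaction stays in the residuals. In the 24 against 72 h scenario the gaps are 105 × 48 = $5,040 and 14.83 × 48 = $712. Fitting their average leaves $2,164 unexplained in each arm, and the SE is still sqrt[1 + 2 × 0.249 × 2,164²/((105² + 14.83²) × 1,475)] = 1.07 times the stratified one.

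The change takes a few sentences in Section 11 and a little more analysis work. It needs no new data, and with exact 50/50 allocation in each stratum the point estimate does not change.
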